#### 5.8.1.3 Secondary Estimand

The only attributes that changes from the definition of the primary estimand is how the handling strategy is adopted for treatment discontinuation.

- Intercurrent events: Treatment discontinuation All available data up to Week 15 including the participants who have discontinued treatment but completed visit after discontinuation ("retrieved dropouts") are used for the analysis ("treatment policy" estimand)
- Missing data: Same missing data imputation will be performed as the primary estimand.

#### 5.8.1.4 Completer Analysis

Completer analysis will also be performed. The only attributes that changes from the definition of the primary estimand is that analysis is done for per protocol analysis set, ie only participants who complete 13-week treatment and with a week 13 assessment and treatment compliance >=80% will be included for analysis. Participants who completed treatment but have week 13 assessment done more than 3 days after last dose date and participants whose weights at week 13 are collect at nonfasted state will be excluded from analysis.

Additional sensitivity analysis may be performed using multiple imputation (MI) approach.

#### **5.8.2** Secondary Efficacy Endpoints

The secondary efficacy endpoints are described in Section 2.2.2.

# 5.8.2.1 Proportion of Participants Achieving ≥ 5% Weight Reduction after 13 Week of Treatment

The same MMRM described for the primary endpoint will be used to address the primary estimand. Missing data will be imputed using MMRM assuming missing at random (MAR) and the imputed value based on the predicted value will be used to classify each subject as a responder or not. A logistical regression using gender and treatment as factors and baseline body weight as covariate will be applied to analyze the imputed data. In addition, cumulative distribution plot and waterfall plot of % weight by treatment change from baseline (Week 0) to Week 13 based on imputed data will be provided.

In addition, the number and percent of participants with weight decreases of  $\geq 5\%$  will be summarize at each timepoint by treatment group. Percentages will be based on the number of participants available at the given timepoint without imputation.

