### **8.3. Subject Withdrawal Criteria**

#### **8.3.1. Procedures for Discontinuation or Withdrawal of a Subject**

##### **8.3.1.1. Discontinuation of Trial Treatment**

Discontinuation of trial product can be decided by either the investigator or the subject. A participant may discontinue his or her participation without giving a reason at any time during the trial.

Participants who discontinue trial product should continue with the scheduled visits and assessments to ensure continued counselling and data collection.

If the subject does not wish to attend the scheduled clinic visits, efforts should be made to have the visits converted to phone contacts. However, all efforts should be made to have the subject attend at least the 'end of treatment' clinic visit containing the final data collection of primary and confirmatory secondary efficacy endpoints, and the 'end of trial' visit.

The 'end of trial' visit is scheduled approximately 2 weeks after the final data collection, to ensure the safety of the subject. If the subject has discontinued trial product >2 weeks prior to the 'end of treatment' visit, and the requirements for the follow-up period prior to the 'end of trial' visit is fulfilled, then the 'end of trial' visit can be performed in combination with 'end of treatment' visit.

If the subject refuses to attend the 'end of treatment' and/or 'end of trial' visit, information about the attempts to follow up with the subject must be documented in the subject's medical record.

The subject must be discontinued from trial product if any of the following applies:

1. Safety concern as judged by the investigator
2. Pregnancy
3. Intention of becoming pregnant
4. Liver function test (LFT) abnormalities meeting specified discontinuation criteria (refer to [Appendix A](#) for discontinuation criteria and instruction on management of LFT abnormalities)
5. Confirmed pancreatitis (see below)

If acute pancreatitis is suspected based on clinical signs and symptoms, blinded study medication should be interrupted immediately, and appropriate diagnostic assessments should be performed.

- A diagnosis of acute pancreatitis requires at least 2 of the following 3 findings :
  - abdominal pain consistent with acute pancreatitis (persistent, severe epigastric pain, frequently radiating to the back); abdominal pain is often associated with nausea and vomiting.
  - serum lipase and/or amylase activity  $\geq 3X$  the laboratory ULN

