#### **Primary Estimand**

For the primary endpoints, the primary estimand for the percentage change from baseline in body weight is defined as the average treatment effect of K-757 alone and the combination of K-757 + K-833 relative to placebo in the mITT analysis population, had they remained on their randomized treatment for the entire planned duration of the trial (“hypothetical” estimand).

A mixed model for repeated measurements (MMRM) analysis will be applied with gender, treatment, visit and treatment-by-visit interaction as fixed effect and baseline body weight as a covariate. The MMRM model will use assessments only from participants who are taking the randomized treatment until end of treatment or until first discontinuation of randomized treatment. An unstructured covariance will be used. If the unstructured covariance structure leads to nonconvergence, Akaike’s information criteria will be used to select the best covariance structure.

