#### 5.1.6 Analysis Visit Windows

For body weight, hemodynamic data (systolic blood pressure, diastolic blood pressure and heart rate) and lab measures (total cholesterol, LDL, HDL, and triglycerides), unscheduled visits and end of treatment visits and follow-up visits for participants who discontinued study drug earlier will be mapped based on analysis visit window below. The analysis visit windows will be exhaustive so that all available values obtained from unscheduled visits, end of treatment visits and follow-up visits for participants who discontinued study drug earlier have the potential to be summarized. No analysis visit windows will be applied for the study scheduled visits.

For other safety measures, analysis visit windowing will not be applied. The visits and time points reported on the electronic case report form (eCRF) will be used.

The following analysis visit windows will be used to map the unscheduled visits, end of treatment visits and follow-up visits for participants who discontinued study drug earlier of body weight.

Visit	Target Day	Analysis Visit Window Based on Study day
Baseline	1	1
Week 4	29	[2, 43]
Week 8	57	[44, 74]

Week 13 for Participants Discontinued Treatment	92	[75, 95]
Week 13 for Participants Completed Treatment	92	[75, Last Dose Date +3]
Week 15 for Participants Discontinued Treatment	105	>95

The following analysis visit windows will be used to map the unscheduled visits, end of treatment visits and follow-up visits for participants who discontinued study drug earlier hemodynamic data (systolic blood pressure, diastolic blood pressure and heart rate).

Visit	Target Day	Analysis Visit Window Based on Study day
Baseline	1	1
Week 1	8	[2,11]
Week 2	15	[12,18]
Week 3	22	[19,25]
Week 4	29	[26, 36]
Week 6	43	[37, 50]
Week 8	57	[51, 64]
Week 10	71	[65, 81]
Week 13 for Participants Discontinued Treatment	92	[82, 95]
Week 13 for Participants Completed Treatment	92	[82, Last Dose Date +3]
Week 15 for Participants Discontinued Treatment	105	>95

In the event of multiple measurements of the same test in the same window, if the measurements are from different visit categories, the priority order is scheduled visit, end of study visits and follow-up visits, then unscheduled visit. For the measurements in the same visit category, the value measured nearest to the target day will be used; if they are at the same distance to the target day, the latest one will be used.

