#### 5.8.1.2 Primary Analysis

A mixed model for repeated measurements (MMRM) analysis will be applied with gender, treatment, visit and treatment-by-visit interaction as fixed effect, and baseline body weight as a covariate. The MMRM model will use assessments only from participants who are taking the randomized treatment until end of treatment if they complete treatment or until 3 days after discontinuation of randomized treatment; scheduled follow up assessment will also be included in analysis. An unstructured covariance will be used. If the unstructured covariance structure leads to nonconvergence, other covariance structures, such as, compound symmetry (CS) and autoregressive (AR(1)) will be used. Akaike's information criteria will be used to select the best covariance structure.

The least squares (LS) means, difference in LS mean (K757 vs placebo, K-757+K-833 vs placebo), the corresponding 95% CI and the p-value will be provided. In addition, descriptive statistics including number of participants, mean and standard error will be provided.

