#### 5.8.3 Subgroup Analyses

To assess the consistency in the treatment effect across different subgroups, subgroup analyses will be performed for the primary efficacy endpoint and secondary efficacy endpoints using same method as primary estimand, with respect to the following:

- Gender (male, female)
- Baseline Body Weight (< 100KG, >= 100 KG)
- BMI (< 35, >= 35)

Forest plot will be presented for subgroup analyses.

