#### 6. Multiplicity

The study tests the primary hypothesis that at least one of the treatment arms is superior to the placebo arm in reducing the body weight calculated as percentage change from baseline after 13 weeks of treatment. Each of the two comparisons between K-757 alone and the combination of K-757+K-833 vs placebo is tested at two-sided alpha of 0.05 with a familywise error rate of 0.10. No other multiplicity adjustment will be performed for secondary and exploratory objectives, which will be tested at two-sided alpha of 0.05.

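### The ≥5% responder analysis fills each missing Week 13 weight with one model prediction and analyses it as observed, so imputation uncertainty is left out and the odds ratio can be biased either way

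*SAP*

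**What the plan says.** SAP Section 5.8.2.1 takes the MMRM of the primary endpoint, imputes missing Week 13 weights under missing at random, and states that "the imputed value based on the predicted value will be used to classify each subject as a responder or not". A logistic regression on gender, treatment and baseline weight is then fitted to the imputed data. The cumulative distribution and waterfall plots use the same imputed data. Percentages without imputation are also given, as a description only. Protocol Section 16.6.2 describes the same analysis but speaks only of an imputed value. The SAP is what makes it the prediction.

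Multiple imputation is optional and is named only for other analyses. SAP Section 5.8.1.4, on the completer analysis of the primary endpoint, says "Additional sensitivity analysis may be performed using multiple imputation (MI) approach". The Protocol allows it under the secondary estimand of the primary endpoint.

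The documents do not settle which weights feed the prediction for someone who stops treatment. The Protocol's primary estimand uses data "until end of treatment or until first discontinuation of randomized treatment". SAP Section 5.8.1.2 uses data "until 3 days after discontinuation of randomized treatment; scheduled follow up assessment will also be included in analysis", without saying whether that follow-up covers discontinuers. Protocol Section 8.3.1.1 adds: "Participants who discontinue trial product should continue with the scheduled visits and assessments to ensure continued counselling and data collection".

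SAP Section 6 puts secondary objectives among those "which will be tested at two-sided alpha of 0.05". SAP Section 5.8.3 says "subgroup analyses will be performed for the primary efficacy endpoint and secondary efficacy endpoints using same method as primary estimand", which carries the rule into the gender, weight and BMI subgroups.

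**The concern.** Filling in a conditional mean does little harm when the target is itself a mean. It does harm when the filled-in value is cut at a threshold. Predictions vary less than real weights, so in an arm whose mean lies beyond -5% too many dropouts become responders, and in an arm whose mean falls short of -5% too few do. The sign of the error in the odds ratio therefore depends on where the arm means lie and on how dropout is split between arms. The documents give neither. The logistic regression also has no means of knowing that some outcomes were predicted, so its standard error is too small.

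At stake are the estimate, interval and test for one of two secondary efficacy endpoints, its subgroup results, and two plots that would show too little spread. The primary MMRM test and the change in kg are not affected.

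**Working it through.** **The plan's own figure.** SAP Section 3.4 gives 150 participants in three arms, SD 4%, difference 4%, 20% dropout, two-sided alpha 0.05 and power above 95%. With 50 × 0.8 = 40 per arm, SE = 4 × √(2/40) = 0.894, and power ≈ Φ(4/0.894 − 1.96) = Φ(2.51) = 99.4%. The statement holds. It concerns the primary endpoint; no responder rate or power is given for this one.

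**Mechanism, by hand.** Let ρ be the correlation between prediction and true Week 13 change. True responder probability is Φ((−5 − μ)/4). A predicted value is classed as a responder with probability Φ((−5 − μ)/(4ρ)). Take assumed means of -6% (active) and -2% (placebo), with 20% dropout in each arm.

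- True rates: Φ(0.25) = 59.9% and Φ(−0.75) = 22.7%, so OR = 5.09.
- ρ = 0.6: dropouts are classed at Φ(0.417) = 66.2% and Φ(−1.25) = 10.6%. Arm rates are 0.8 × 59.9 + 0.2 × 66.2 = 61.1% and 0.8 × 22.7 + 0.2 × 10.6 = 20.2%; OR = 6.20.
- ρ = 0.85: OR = 5.39. ρ = 0, where every dropout takes the arm mean: OR = 9.55.

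Now take means of -4% and 0%, with 30% active and 10% placebo dropout. The true OR is 5.67. At ρ = 0 no dropout is a responder, so the rates are 0.7 × 40.1 = 28.1% and 0.9 × 10.6 = 9.5%, and OR = 3.72. The direction has reversed. At ρ = 0.97 the ratio of estimated to true OR is 1.00 to 1.02 in every setting tried.

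**Simulation of the planned model.** The SAP 5.8.1.2 model with unstructured covariance was followed by the SAP 5.8.2.1 regression, with 150,000 per arm. Assumed:

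- SDs at Weeks 4/8/13/15 of 2/3/4/4;
- correlations of 0.80 (Weeks 4–8), 0.85 (8–13), 0.65 (4–13) and 0.90 to 0.95 (13–15);
- gender and baseline weight explaining 10% of Week 13 variance;
- dropout uniform over Days 1 to 91, and no regain off drug.

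Odds ratios (means and dropout as active/placebo):

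| Means; dropout | Complete data | No later weight | Exit weight for all | Day 105 weight for all |
|---|---|---|---|---|
| -6/-2; 20/20% | 5.6 | 7.4 | 6.3 | 5.7–5.8 |
| -4/0; 30/10% | 6.23 | 5.55 | 6.26 | 6.27–6.32 |
| -3/-1; 20/20% | 2.5 | 2.5–2.6 | 2.5–2.6 | 2.5–2.6 |
| -3/-1; 30/10% | 2.5 | 2.2 | 2.4 | 2.5 |
| -2/-2; 30/10% | 1.0 | 0.86 | 0.92 | 0.97–0.98 |

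In the first row, participants lacking Week 13 are imputed as responders in 74%/10%, 64%/14% and 61%/21% of cases, against a true 60%/23%. Covariate adjustment does not remove the bias: if the covariates explain nothing, the row reads 6.6 / 5.6 / 5.1–5.2 against 5.1.

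**Intervals at 50 per arm** (10,000 trials; Week 13–15 correlation 0.90; same column order):

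| | Complete data | No later weight | Exit weight | Day 105 weight |
|---|---|---|---|---|
| Coverage, -6/-2 | 95.2% | 89.2% | 92.6% | 94.5% |
| Mean SE vs actual SD of log OR, -6/-2 | – | 0.50 vs 0.56 | 0.49 vs 0.54 | 0.48 vs 0.51 |
| Coverage, -4/0 | 96.6% | 93.4% | 95.5% | 96.3% |
| Null rejection, -2/-2 | 4.6% | 6.7% | 6.2% | 5.2% |

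Multiple imputation (1,000 trials, 20 draws, Rubin's rules) gives 95.5% to 96.0% coverage in the -6/-2 case.

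**Second simulation, other assumptions** (two arms; SDs 1.8/3.0/4.0/4.1; correlations with Week 13 of 0.6, 0.85 and 0.97 for Weeks 4, 8 and 15; 2,000 trials). At -6/-2 with no later weights, the median OR is 7.17 against 5.29 with complete data, and coverage is 87.8%. Multiple imputation gives 5.37 and 95.8%. With both means at -4%, nearer the threshold, 20% dropout per arm gives 10.2% false rejections, against 5.8% with complete data and 4.2% with multiple imputation. If the predicted value were read as the arm's model mean, ignoring the participant's own earlier weights, the median OR at -6/-2 would be about 10.

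**The case against.** The largest figures assume that no dropout supplies an exit or follow-up weight. The Protocol works against that: Section 8.3.1.1 asks discontinuers to keep attending, Section 8.3.1.2 requires that anyone leaving be asked for end-of-treatment assessments, and under SAP Section 5.1.6 "end of treatment visits and follow-up visits for participants who discontinued study drug earlier will be mapped based on analysis visit window below". Even the worst case is modest against sampling error: ln(7.4/5.6)/0.50 ≈ 0.56 of a standard error, falling to ln(6.3/5.6)/0.49 ≈ 0.24 with exit weights. The endpoint is secondary in a Phase 2 trial that accepts a familywise error rate of 0.10, and unimputed percentages are reported too.

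This limits the size and is why the point is not graded higher. It does not rescue the method. Exit weights for everyone still leave coverage at 92.6% at -6/-2, attendance cannot be known in advance, and descriptive percentages do not correct a test.

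A further objection is that the Day 105 column assumes no regain off drug, while Protocol Section 5.4 describes satiety effects that come and go quickly. If 10% to 50% of the drug effect were lost per 14 days off drug (an assumption), the unadjusted OR at -6/-2 with Day 105 weights would be about 4.4 to 4.7 against 5.0 to 5.1. That is a fair caution, but it concerns which weights belong in a model for the hypothetical estimand. Multiple imputation would not cure it, and it does not justify single prediction.

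**Conclusion.** The rule is wrong as written and should be fixed. That imputation uncertainty is omitted, and that a thresholded prediction misclassifies dropouts, follows from the text and does not depend on missing at random failing.

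The size is conditional. The error is clear when the arm means lie on either side of -5% and dropouts supply few later weights: the OR is then about a third too high (7.4/5.6 = 1.32) and the standard error about 11% too small (0.50/0.56 = 0.89). If the active mean falls short of -5% and the active arm loses more participants, the OR can be too low. In the other cases examined the error is small, although false rejections rise when both means sit near the threshold.

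Only the SD, the 4-point difference, the 20% dropout and the sample size come from the documents. Arm means, earlier SDs, correlations, covariate strength, the timing and split of dropout, attendance and absence of regain are assumed. Confidence is high in the mechanism and lower in any single figure.

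**What to change.** Before unblinding, amend SAP Section 5.8.2.1:

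- Replace the single predicted value with multiple imputation under the same missing-at-random model, drawing with both residual variance and parameter uncertainty.
- Classify ≥5% loss within each imputed dataset, fit the same logistic regression, and combine with Rubin's rules. The number of imputations is the sponsor's choice.
- Use the same method for the responder subgroups in Section 5.8.3.
- Do not base the waterfall and cumulative distribution plots on single predictions. Keep the unimputed percentages as a descriptive check.

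Alongside this, reconcile the Protocol's primary estimand text with SAP Section 5.8.1.2 on which weights after discontinuation enter the model, since the imputation depends on it.

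The cost is SAP wording and some standard programming, with no new data or visits. At -6/-2 the mean SE of the log OR rises from 0.50 to 0.52 with no later weights, and from 0.48 to 0.50 with a Day 105 weight for all.

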#### 5.8.2.2 Change from Baseline in Body Weight (kg) after 13 Weeks of Treatment

The change from baseline will be analyzed to address the primary estimand using the same MMRM described for the primary endpoint.

#### 5.8.3 Subgroup Analyses

To assess the consistency in the treatment effect across different subgroups, subgroup analyses will be performed for the primary efficacy endpoint and secondary efficacy endpoints using same method as primary estimand, with respect to the following:

- Gender (male, female)
- Baseline Body Weight (< 100KG, >= 100 KG)
- BMI (< 35, >= 35)

Forest plot will be presented for subgroup analyses.

#### **5.8.4** Exploratory Endpoints

The exploratory endpoints are described in Section 2.2.3.

#### 5.8.4.1 Change from Baseline in Hemodynamic parameters after 13 Weeks of Treatment

The hemodynamic parameters include systolic blood pressure, diastolic blood pressure and heart rate.

The change from baseline in hemodynamic parameters will be analyzed using the same MMRM approach described for the continuous secondary endpoints. For triplicate measurements, the average value will be analyzed.

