### **16.6.3. Exploratory Endpoints**

The exploratory endpoints will be analyzed using the same approach described for the secondary endpoint.

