# 5.8.4.2 Change from Baseline in Total Cholesterol, LDL, HDL, and Triglycerides after 13 Weeks of treatment

Post-baseline Last observation carried forward (LOCF) approach will be used to impute missing value at Week 13. Only assessments for subjects who are on treatment for more than 28 days, collected on or before treatment discontinuation + 3 days will be used for LOCF. The change from baseline in total cholesterol, LDL and HDL will be analyzed using ANCOVA model with change from baseline at Week 13 as the response variable, treatment, gender, baseline value as covariates.

Triglycerides is not expected to be normally distributed. The Hodge-Lehmann method will be used to estimate the median difference with 90% CI between treatment groups. A Wilcoxon rank sum test will be performed.

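### Read literally, the blood pressure and heart rate models adjust only for baseline body weight; adding each parameter's own baseline would sharpen these exploratory contrasts at almost no cost

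*SAP*

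**What the plan says.** The hemodynamic model is defined by a chain of cross-references:

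- **SAP 5.8.4.1:** change from baseline in the hemodynamic parameters "will be analyzed using the same MMRM approach described for the continuous secondary endpoints". Triplicate readings are averaged.
- **SAP 5.8.2.2**, the only continuous secondary efficacy endpoint (weight in kg): "The change from baseline will be analyzed to address the primary estimand using the same MMRM described for the primary endpoint".
- **SAP 5.8.1.2**, the primary model, has "gender, treatment, visit and treatment-by-visit interaction as fixed effect, and baseline body weight as a covariate".

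The Protocol runs in parallel. Section 16.6.3 says "The exploratory endpoints will be analyzed using the same approach described for the secondary endpoint", 16.6.2 refers back to the primary model, and 16.6.1 gives the terms as "gender, treatment, visit and treatment-by-visit interaction as fixed effect and baseline body weight as a covariate".

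Neither document says that the covariate changes with the endpoint. The baseline blood pressure or heart rate enters only by subtraction, because SAP 5.1.2 defines change as the post-baseline value minus the baseline value. In the next subsection, SAP 5.8.4.2, total cholesterol, LDL and HDL are given an "ANCOVA model with change from baseline at Week 13 as the response variable, treatment, gender, baseline value as covariates".

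**The concern.** For weight, baseline body weight is the endpoint's own baseline, so the primary model is properly specified. Carried over unchanged to blood pressure and heart rate, the same covariate becomes a different variable, and the usual strongest predictor of change in a parameter, its own starting value, drops out.

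Two things follow. The treatment contrast generally has a wider interval than the data allow. And if the arms differ by chance in baseline pressure or rate, part of that difference passes into the estimated effect. Randomization is stratified by gender only (Protocol 7.3.1, SAP 3.2), so the design does not balance these baselines.

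The stakes are modest but real. Protocol 5.3 lists heart rate and blood pressure among the measures that incretin-based therapies sometimes affect. SAP Section 6 tests exploratory objectives at two-sided 0.05 with no multiplicity adjustment. Avoidable noise could hide a change, and a baseline imbalance could resemble one.

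**Working it through.** **The plan's own figure.** No precision or power is stated for blood pressure or heart rate. The only design figure is more than 95% power for weight (Protocol 16.2, SAP 3.4). With 50 x 0.8 = 40 completers per arm, a difference of 4 and SD of 4, the standardized difference is 4 / (4 x sqrt(2/40)) = 4.47. Power is then 99.4% (99.3% with the t distribution), so the statement is reproduced. It supplies the 40 per arm used below.

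**Inputs not in the documents (assumed).** The correlation rho between baseline and Week 13, shown over 0.4 to 0.8; the ratio k of baseline SD to follow-up SD, first set to 1; and, for illustration in mmHg only, a follow-up systolic SD of 12. The formulas treat Week 13 as a single visit and take body weight as explaining little of the change.

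**Formulas.** With follow-up SD s and baseline SD ks:

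- Variance of the change score: s^2 x (1 + k^2 - 2k x rho) = s^2 x [(1 - rho^2) + (k - rho)^2]
- Variance after own-baseline adjustment: s^2 x (1 - rho^2)
- Shift in the unadjusted contrast from a baseline imbalance D: -(1 - rho/k) x D

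The extra term (k - rho)^2 cannot be negative, so the change score is never more precise, apart from the one degree of freedom the covariate costs. At k = 1 the variance ratio is (1 - rho^2) / [2(1 - rho)] = (1 + rho)/2, and the shift is -(1 - rho) x D.

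**Results at k = 1.**

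| rho | Variance ratio | SE smaller by | 40 per arm as planned equals, with own baseline | Shift per unit of imbalance |
|---|---|---|---|---|
| 0.4 | 0.70 | 16.3% | 28 | -0.6 |
| 0.5 | 0.75 | 13.4% | 30 | -0.5 |
| 0.6 | 0.80 | 10.6% | 32 | -0.4 |
| 0.7 | 0.85 | 7.8% | 34 | -0.3 |
| 0.8 | 0.90 | 5.1% | 36 | -0.2 |

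**In mmHg.** At SD 12, rho 0.5 and 40 per arm, the SE is 12 x sqrt(2 x 0.5) x sqrt(2/40) = 2.68 without own baseline and 12 x sqrt(0.75) x sqrt(2/40) = 2.32 with it. A one-SE baseline imbalance is 12 x sqrt(2/40) = 2.68 mmHg and would move the contrast by 0.5 x 2.68 = 1.34 mmHg.

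**Simulation check.** Single visit, 40 per arm, 6,000 runs per rho, equal variances, with gender and baseline body weight in the comparator model and an assumed correlation of 0.15 between weight and blood pressure. The variance ratios were 0.695, 0.788 and 0.895 at rho 0.4, 0.6 and 0.8, against 0.70, 0.80 and 0.90 by formula. The slopes on baseline imbalance were -0.58, -0.40 and -0.20 with body weight, and 0.00 with own baseline. The mean error was about 0 in both models.

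**Sensitivity to unequal variances.** At k = 0.8 and rho = 0.6 the ratio is 0.64 / (0.64 + 0.04) = 0.94 rather than 0.80. At k = rho there is no gain.

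**The case against.** **The intent may already be right.** In the source model baseline weight is the endpoint's own baseline, so borrowing the approach could mean using the baseline of whatever parameter is analyzed. That reading is reasonable, but the primary model names body weight explicitly and nothing tells the programmer to replace it. If own baseline is intended, the sentence is still needed.

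**A reader might infer that the SAP contradicts itself.** The documents do not support that. Section 5.8.4.2 introduces a different model (ANCOVA with last observation carried forward), so it has to list its terms, whereas 5.8.4.1 works by cross-reference. Nor do all the lipids receive own-baseline adjustment: triglycerides get a Hodges-Lehmann estimate and a rank-sum test with no stated baseline term. What 5.8.4.2 does show is that the authors name the covariate when they spell out a model.

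**A reader might infer bias from uncorrected regression to the mean.** That also fails. Regression to the mean acts on all randomized arms alike on average, and the simulated mean error was about zero. Only a chance imbalance in the particular trial is carried through, and the planned standard error already reflects that variability. The loss is one of efficiency.

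**The size is uncertain.** This stands. Averaging triplicate readings under the standardized conditions of Protocol 14.2 should raise rho. Exclusion Criterion 33 (systolic above 160 or diastolic above 95 mmHg) may narrow the baseline spread. Either would reduce the gain.

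**The endpoints are exploratory.** This stands too. They carry no sample-size claim, and vital signs are also summarized descriptively under SAP 5.11.3.

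**Conclusion.** The point holds as a nearly free improvement to exploratory analyses. Followed as written, the plan gives valid blood pressure and heart rate contrasts that are generally less precise than they need be. With equal variances and rho between 0.4 and 0.8, both assumed, the own-baseline SE is about 16% to 5% smaller; at k = 0.8 and rho = 0.6 it is only about 3% smaller (1 - sqrt(0.94)). The direction does not depend on these assumptions, but the size does. The primary endpoint and the kg-weight endpoint are not affected.

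**What to change.** In SAP 5.8.4.1, state that each systolic, diastolic and heart-rate MMRM includes that parameter's own baseline (mean of the triplicate) as a covariate, in place of or in addition to baseline body weight. A baseline-by-visit term is optional and would let the slope differ between visits.

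No new data are needed, because Protocol Table 2 already schedules blood pressure and heart rate at Visit 2. If this only clarifies what was meant, one sentence is enough. If the literal reading is taken as the plan, Protocol 16.6.3 points to the body-weight covariate as well; the change should then also be recorded in SAP Section 8, which at present reports no departures from the Protocol. Either way it should be settled before database lock.
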